8.4.2 Documenting, Assessing, Recording, and Reporting Events

ALL AEs, including those that may appear to have a non-study cause (see "Causality" below), will be documented (e.g., on the clinical chart/progress notes/clinical laboratory record), recorded (e.g., in the study-specified CRF/research database), and reported (e.g., cumulatively from the research database, or according to protocol-specified expedited reporting mechanism) to the sponsor from the time informed consent is obtained through the timeframe specified below. At each contact with the subject, information regarding AEs will be elicited by open-ended questioning and examinations.

AEs and SAEs will generally be recorded, assessed, and reported according to the timeframes outlined in Table 2.

Version Date: 14 March 2024

Table 2. Standard event recording, assessment, and reporting timeframes.

Event type	Record, assess, and report through
Related SAEs	End of subject participation in study, or if study personnel become aware thereafter
Unrelated SAEs	End of subject participation in study
Related non-serious AEs of grade 1 to 3	End of subject participation in study
All other related non- serious AEs	End of subject participation in study
Unrelated non-serious AEs	End of subject participation in study

8.4.2.1 Investigator Assessment of Adverse Events

The investigator will assess all AEs with respect to **seriousness** (according to SAE definition above), **severity** (intensity or grade, see below), and **causality** (relationship to study agent and relationship to participation in the research, see below).

8.4.2.1.1 Severity Grading

The investigator will grade the severity of fever (by non-oral temperature reading) and each blood laboratory testing AE according to the "Mali Adverse Event Grading Scale" provided in Appendix B (separate tables provided for adults and children). Events that are not gradable using this table (e.g., urinalysis abnormalities) will be graded according to the "Guidance for Industry: Toxicity Grading Scale for Healthy Adult and Adolescent Volunteers Enrolled in Preventive Vaccine Clinical Trials" which can be found at: https://www.fda.gov/regulatory-information/search-fda-guidance-documents/toxicity-grading-scale-healthy-adult-and-adolescent-volunteers-enrolled-preventive-vaccine-clinical

Events that are NOT gradable using either of the above specified tables will be graded as follows:

- Mild = grade 1
- Moderate = grade 2
- Severe = grade 3
- Potentially life threatening = grade 4
- Death = grade 5

NOTE: A subject death should always be reported as grade 5.

Version Date: 14 March 2024

8.4.2.1.1.1 Laboratory Value Assessment and Clinical Significance Criteria

Except as specified below, ALL abnormal lab values of grade 1 or above are REPORTABLE. Grade 1 and 2 abnormal laboratory values are considered CLINICALLY SIGNIFICANT, and are to be recorded in the research database, and reported, if they meet ONE or more of the following criteria:

- result in a study agent dosage adjustment, interruption, or discontinuation
- are accompanied by clinically abnormal signs or symptoms that are likely related to the laboratory abnormality (e.g., clinical jaundice)
- indicate a possible organ toxicity (e.g., elevated serum Cr)
- result in additional/repeat testing or medical intervention (procedures/treatments) (e.g., ECG to evaluate arrhythmia potential with a high serum potassium; one or more ECGs to assess an elevated troponin level; potassium supplementation for hypokalemia)
- indicates possible over-dosage
- are considered clinically significant by the investigator or SMM

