8.4 Safety Definitions, Management, and Sponsor Reporting

8.4.1 Definitions

Adverse Event: An AE is any untoward or unfavorable medical occurrence in a human subject, including any abnormal sign (e.g., abnormal physical exam or laboratory finding), symptom, or disease, temporally associated with the subject's participation in the research, whether or not considered related to the research.

Adverse Reaction: An AR means any AE caused (see "Causality" below) by a study agent. ARs are a subset of all suspected adverse reactions (SARs; defined below) where there is reason to conclude that the study agent caused the event.

Version Date: 14 March 2024

Suspected Adverse Reaction: SAR means any AE for which there is a reasonable possibility that the study agent caused the AE.

Per US FDA guidance:

For the purposes of IND safety reporting, "reasonable possibility" means there is evidence to suggest a causal (see "Causality" below) relationship between the study agent and the AE. A SAR implies a lesser degree of certainty about causality than an AR, which means any AE caused by a study agent.

SARs are the subset of all AEs for which there is a reasonable possibility that the study agent caused (see "Causality" below) the event. Inherent in this definition, and in the requirement to report SARs, is the need for the sponsor to evaluate the available evidence and make a judgment about the likelihood that the study agent actually caused the AE.

The sponsor is responsible for making the causality judgment.

Serious Adverse Event: An SAE:

- is an AE that results in death.
- is an AE that is life-threatening event (places the subject at immediate risk of death from the event as it occurred).
- is an AE that requires inpatient hospitalization or prolongs an existing hospitalization. NOTE:
 - Hospitalization is considered required if outpatient treatment would generally be considered inappropriate.
 - o Same-day surgical procedures that are required to address an AE are considered hospitalizations, even if they do not involve an overnight admission.
 - O Hospitalization due to a condition that has not worsened and that pre-dates study participation (e.g., elective correction of an unchanged baseline skin lesion), or due to social circumstance (e.g., prolonged stay to arrange aftercare), or that is planned/required "per protocol" AND that proceeds without prolongation or complication, is NOT considered an SAE by this criterion.

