8.4.2.2 Recording of Events

AEs will be promptly recorded in the research database, regardless of possible relationship to study interventions. If a diagnosis is clinically evident (or subsequently determined), the diagnosis rather than the individual signs and symptoms or laboratory abnormalities will be recorded as the AE. The investigator will review events regularly to ensure they have been captured correctly and to perform assessment of events individually and cumulatively to assess possible safety trends.

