9.5.5 Safety Analyses

Safety analysis will be primarily MITT where individuals who receive assignment but do not receive any product are excluded. Because of blinding and the brief length of time between assignment and administration, such cases will be very few. In the rare case of subjects receiving a regimen different from assignment, an as-treated analysis will be additionally performed where subjects will be analyzed according to the product they actually receive.

Safety data will be presented by line listing and tables at the individual level to provide details on safety events such as severity, duration, and relationship to study product. The number and percentage of subjects with 1 or more AE(s) will be summarized by dose arm along with the exact 95% CIs of the AE rate. The number and percentage of subjects under each AE will be

Version Date: 14 March 2024

additionally reported. For subjects experiencing more than 1 AE, the subjects will be counted once under the event of highest severity.

In the efficacy study, comparisons between the dose arms and the control arm will be additionally performed in terms of the proportions of solicited AEs, related AEs, and SAEs.

In the rare case of subjects receiving a regimen different from assignment, a per-protocol analysis will be performed as a secondary analysis, which will include subjects according to the product they actually receive in the study.

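### Grade 1-2 laboratory abnormalities reach the safety tables only through a conditional recording rule that the general AE sections do not mention, and section 9.5.5 plans no table from the measured values

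*Combined protocol and SAP*

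**What the plan says.** The general rules carry no grade or significance condition. Section 8.4.1 defines an AE as an unfavourable medical occurrence, "including any abnormal sign (e.g., abnormal physical exam or laboratory finding), symptom, or disease". Section 8.4.2 applies documentation, recording and reporting to "ALL AEs, including those that may appear to have a non-study cause". Section 8.4.2.2 adds that "AEs will be promptly recorded in the research database, regardless of possible relationship to study interventions".

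The laboratory rule in section 8.4.2.1.1.1 is narrower. It opens with "Except as specified below, ALL abnormal lab values of grade 1 or above are REPORTABLE". For the two lowest grades it then sets a separate rule: "Grade 1 and 2 abnormal laboratory values are considered CLINICALLY SIGNIFICANT, and are to be recorded in the research database", but on condition that at least one of six criteria holds. In paraphrase, the six criteria are:

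- a change to study agent dosing;
- accompanying signs or symptoms likely to be linked to the value;
- possible organ toxicity, with raised creatinine as the example;
- further testing or medical intervention;
- possible overdose;
- values that "are considered clinically significant by the investigator or SMM".

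Section 9.5.2 sends the primary safety endpoint to section 9.5.5, where "The number and percentage of subjects with 1 or more AE(s) will be summarized by dose arm along with the exact 95% CIs". Section 9.5.5 neither excludes laboratory AEs nor plans a table of graded laboratory values. The schedules in section 1.3 require CBC with differential, ALT and creatinine on Days 0, 3, 7 and 14 in every cohort, with the Day 0 sample taken before dosing.

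**The concern.** The same laboratory result is an AE record under one set of sections and may be no record under another. Take a child without symptoms whose Day 3 neutrophil count lies in the grade 2 band of Appendix C (0.50 to 0.74 x 10³/µL). Under 8.4.1, 8.4.2 and 8.4.2.2 this is an AE to be entered. Under 8.4.2.1.1.1 it is entered only if someone orders a further test, suspects organ toxicity, links a symptom to it, intervenes, or judges it significant.

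Since section 9.5.5 works from AE records, a mild or moderate laboratory effect of L9LS would show only as far as staff acted on it. This matters most in the dose-escalation arms of 6 and 9 subjects, where one visible case carries weight. The protocol already pays for the measurements that would show the effect directly.

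**Working it through.** **Which values the filter reaches.** Appendix C grades six analytes: haemoglobin, white cells (high and low), neutrophils, platelets, creatinine and ALT. Two draws, Days 3 and 7, are planned in the 7-day window, so 6 x 2 = 12 graded measurements per child. The Day 7 visit has a ±2-day window, so some of those draws can fall later. Grade 3 and above is not filtered. Raised creatinine is the named example of a recordable finding, and a raised ALT could plausibly pass as possible organ toxicity. The filter therefore falls mainly on the four haematology analytes, or 4 x 2 = 8 measurements.

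**How much judgment remains.** Section 6.1.2.3 states that each subject receives one dose with no modifications, so the dosing criterion has almost no role. The other criteria depend largely on whether staff request a repeat test, intervene, attribute symptoms, suspect toxicity or overdose, or consider the value significant.

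**The plan's own detection figures.** The documents give no rate of laboratory abnormality. Section 9.2.1 does give true AE rates at which the chance of seeing at least one AE exceeds 90%. From 1 − (1 − p)ⁿ = 0.90, p = 1 − 0.1^(1/n):

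- n = 6: 0.3187 (stated 0.319)
- n = 9: 0.2257 (stated 0.226)

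Both reproduce.

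**Effect of partial recording (illustration).** Let p be the true proportion of subjects with a grade 1-2 laboratory abnormality and f the fraction recorded. Both are assumptions. The recorded rate is pf, and the chance of at least one record is 1 − (1 − pf)ⁿ. With p = 0.20:

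| f | recorded rate | n = 6 | n = 9 | expected of 75 |
|---|---|---|---|---|
| 1.00 | 0.20 | 0.738 | 0.866 | 15.0 |
| 0.75 | 0.15 | 0.623 | 0.768 | 11.3 |
| 0.50 | 0.10 | 0.469 | 0.613 | 7.5 |
| 0.25 | 0.05 | 0.265 | 0.370 | 3.8 |

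For n = 9, going from f = 1 to f = 0.25 lowers the chance from 0.613 to 0.204 if p = 0.10, and from 0.960 to 0.504 if p = 0.30.

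Put the other way, 90% detection of these events needs a true rate of 0.2257 / f. At f = 0.50 that is 0.451 for n = 9, and 0.3187 / 0.50 = 0.637 for n = 6.

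**Against sampling error in the efficacy study.** The exact 95% interval is 11.6% to 30.8% for 15 of 75, and 4.7% to 19.9% for 8 of 75. Halving the recorded count from an assumed 20% moves the estimate to just below the lower limit of the fully recorded interval. If most abnormalities meet a criterion, the shift stays inside sampling error.

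**The case against.** **The rule is a deliberate exception.** It sits inside 8.4.2 and says that it is one. A specific nested rule normally governs its parent, and the criteria can be read as saying when a mild value is unfavourable enough to be an AE. This largely stands: the intent is clear. What remains is that 8.4.1, 8.4.2 and 8.4.2.2 do not refer to the exception, and that 9.5.5 offers nothing to replace the values it removes.

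**The primary endpoint may not be involved.** A reader might infer that the primary safety rates themselves depend on investigator filtering. The documents do not support that as fact. The endpoint covers local and systemic AEs within 7 days, and the reactogenicity lists in sections 1.3 and 6.1.2.4 contain no laboratory item. Equally, nothing excludes laboratory AEs. If they are outside the endpoint, the effect falls on the overall AE tables.

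**The arms are not biased against each other.** A reader might also infer a distorted comparison. Section 6.3.2 keeps those who assess the children blinded, so filtering should be broadly equal across the paediatric arms. The between-arm comparisons in 9.5.5 cover solicited AEs, related AEs and SAEs; of these, mainly related AEs could be affected. The adult arms are open label but have no placebo comparison.

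**Neutropenia may be recorded anyway.** Appendix C, footnote 3, says neutropenias are graded and followed, and extra testing would meet a criterion. This stands in part. A low Day 3 value is measured again on Days 7 and 14 by schedule, so it can be followed with no extra test ordered.

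**Conclusion.** The point holds as a gap in safety reporting and a missing cross-reference, not as a demonstrated defect in the primary endpoint. Grade 1-2 haematology changes can be absent from the by-arm tables although they are measured in every subject. The consequence is lower absolute rates and lower sensitivity, with the largest cost in arms of 6 and 9.

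The size is unknown. The figures above rest on assumed values of p (0.10 to 0.30) and f (0.25 to 1), and the effect vanishes as f approaches 1. Treating every child with a mild abnormality as lost would be an upper bound that the documents do not support, because some will meet a criterion. The change is worth making because it is cheap and removes the dependence on f altogether.

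**What to change.** Add to section 9.5.5: laboratory safety is summarised by arm from the measured values, as worst post-dose grade (Appendix B for adults, Appendix C for children) and as shift from the Day 0 grade, in a table separate from investigator-recorded AEs. The shift is needed because exclusion criteria 6 and 7 in section 5.2 allow entry with out-of-range values judged not clinically significant.

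Reconcile 8.4.1, 8.4.2, 8.4.2.2 and 8.4.2.1.1.1 so that one rule says which laboratory values become AE records, and state whether laboratory AEs are part of the primary safety endpoint.

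The cost is one programmed table, with no new data and no change to care. Displayed laboratory abnormality rates will rise in all arms, so the text should say that they come from measured values. Year 1 unblinding was planned for about March/April 2023, before this version's date of 14 March 2024, so the Year 1 table should be labelled as added after that planned date.

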8.4.2.1.2 Causality

Causality (likelihood that the event is caused by the study agents) will be assessed by the principal investigator or designee considering the factors listed under the following categories:

Definitely Related

- reasonable temporal relationship
- follows a known response pattern
- clear evidence to suggest a causal relationship
- there is no alternative etiology

Probably Related

- reasonable temporal relationship
- follows a suspected response pattern (based on similar agents)
- no evidence of a more likely alternative etiology

Possibly Related

- reasonable temporal relationship
- little evidence for a more likely alternative etiology

Version Date: 14 March 2024

Unlikely Related

• does not have a reasonable temporal relationship

AND/OR

• there is good evidence for a more likely alternative etiology

Not Related

• does not have a temporal relationship

AND/OR

• definitely due to an alternative etiology

Note: Other factors (e.g., dechallenge, rechallenge, if applicable) should also be considered for each causality category when appropriate. Causality assessment is based on available information at the time of the assessment of the AE. The investigator may revise the causality assessment as additional information becomes available.

Causality assessment will be reviewed by the sponsor. The sponsor may make a separate and final determination on the "reasonable possibility" that the event was "related" (comprising definitely, probably, and possibly related) or "unrelated" (comprising unlikely and not related) to the study agent, in keeping with applicable (US FDA) guidance on sponsor IND safety reporting.

8.4.2.2 Recording of Events

AEs will be promptly recorded in the research database, regardless of possible relationship to study interventions. If a diagnosis is clinically evident (or subsequently determined), the diagnosis rather than the individual signs and symptoms or laboratory abnormalities will be recorded as the AE. The investigator will review events regularly to ensure they have been captured correctly and to perform assessment of events individually and cumulatively to assess possible safety trends.

8.4.2.3 Investigator Reporting Responsibilities

The principal investigators and/or equally qualified designees will check daily for events that may require expedited reporting.

The principal investigators and/or equally qualified designees will also monitor all accumulating data no less than weekly, or according to superseding NIH or NIAID policy, whichever is more frequent.

Data will be reviewed by the principal investigators/designees on a regular basis for accuracy and completeness.

Version Date: 14 March 2024

Data will be submitted to the sponsor in keeping with all applicable agreements and when requested, such as for periodic safety assessments, review of IND annual reports, review of IND safety reports, and preparation of final study reports.

The principal investigators and/or other study designee will ensure prompt reporting to safety oversight bodies (e.g., Clinical Safety Office [CSO], DSMB), regulatory entities, and stakeholders as specified below, and according to any additional requirements or agreements.

8.4.2.3.1 Adverse Events

Unless otherwise specified above, AE data will be entered into the research database no less than every other week and will include all data through 1 week prior to database entry.

8.4.2.3.2 Serious Adverse Events (Expedited Reporting)

Unless otherwise specified above, all SAEs (regardless of relationship and whether or not they are also UPs) must be reported to the CSO as specified by the CSO (e.g., Research Electronic Data Capture [REDCap] system; use the Safety Expedited Report Form [SERF]/email if REDCap is not available). If the preferred/indicated mechanism for reporting is not available, the CSO/SMM should be contacted by telephone, fax, or other reasonable mechanism to avoid delays in reporting.

CSO CONTACT INFORMATION:

Clinical Safety Office [name] [contact]

[contact]

Email: [contact]

https://crimsonredcap.cc.nih.gov/redcap/index.php

Unless otherwise specified above, deaths and immediately life-threatening SAEs must be reported to the CSO promptly, and no later than the **first business day** following the day of study personnel awareness.

All other SAEs must be reported to the CSO no later than the **third business day** following the day of study personnel awareness.

If an individual subject experiences multiple SAEs in a closely timed/overlapping "cause-and-effect" (cascade) sequence, the principal investigators, after careful evaluation, will report ONLY primary/precipitating event(s) individually. SAEs that are determined to be definitely secondary to other SAEs will be detailed in the narrative portion of the report of the relevant

Version Date: 14 March 2024

primary/precipitating SAE. A clinical rationale and findings to support such reporting should be part of the narrative.

For each SAE report, the research database entry MUST match the corresponding entries on the SAE report (e.g., start and stop dates, event type, relationship, and grade), and **must be updated if necessary** (e.g., if the SAE report was generated after the corresponding AE was entered in the research database).

Unless otherwise specified above, SAEs that have not resolved by the end of the per-protocol follow-up period for the subject are to be followed until final outcome is known (to the degree permitted by the EC-approved informed consent form). If it is not possible to obtain a final outcome for an SAE (e.g., the subject is lost to follow-up), and to update the CSO, the last known status and the reason a final outcome could not be obtained will be recorded by the investigator on an SAE report update and the CRF.

8.4.2.3.3 Unanticipated Problems

Unless otherwise specified above, UPs (as defined in this protocol, or as defined by the EC of record, whichever definition is more conservative) that are also AEs or SAEs, must be reported to the CSO (by REDCap, or by email and SERF if REDCap is not available) no later than when they are due to be reported to the EC.

UPnonAEs are NOT reported to the CSO but must be reported to the Clinical Trials Management (CTM) group according to their requirements and preferred methods. If the UPnonAE raises a significant potential subject safety concern, the SMM should be consulted by email or phone no later than when reports are made to the CTM.

8.4.2.3.4 Pregnancy

Unless otherwise specified above, all pregnancies will be reported (by REDCap, or by email and SERF if REDCap is not available) to the CSO no later than the first business day following the day of study personnel awareness.

Pregnancy outcome data (e.g., delivery outcome, spontaneous or elective termination of the pregnancy) will be reported to the CSO no later than the third business day following the day of study personnel awareness (by REDCap, or by email and SERF if REDCap is not available). Pregnancy itself is not an AE. Events that meet AE or SAE criteria in relation to pregnancy, delivery, or the conceptus/neonate (see section 8.4.1) are reportable (by REDCap, or by email and SERF if REDCap is not available).

In the event of pregnancy in a study subject exposed to study agent, the following actions will be taken, with the goal of ensuring maternal and fetal well-being, in consultation with the SMM, ISM, and DSMB:

Version Date: 14 March 2024

• Sample collection will continue per guidelines below:

- o Only proceed with PK blood draw if subject's hemoglobin value is ≥8.0 gm/dL (assessed via venipuncture collection of 0.5 mL of blood).
- PK samples (4-8 mL) will be collected according to the regular study schedule (see sections 1.3.1 and 1.3.2).
- The venipuncture used to measure hemoglobin at the visits specified above will also be used to collect blood smears for detection of Pf infection by microscopic examination, and dried blood spots for Pf RT-PCR.
- Serum storage samples will not be drawn if a subject becomes pregnant.
- Continue to follow for safety on a monthly basis for the duration of the pregnancy and for a period of up to 6 months (per investigator discretion) following delivery for assessment of the neonate.
- Request to unblind the subject, if applicable, AND if doing so would offer a benefit to the subject.
- Report, no later than the first business day after study personnel awareness, to the ISM and DSMB.
- Advise subject to notify the obstetrician of study participation and study agent exposure, providing contact information for the obstetrician to contact the study principal investigator, should this be required, and with the subject's consent.

